## TEAEs for Repeat Treatment

Summary tables by study limb dose across all Treatment Cycles 1, 2, 3, and 4 will be provided as described above.

For Treatment Cycles 2, 3, and 4 the following tables by **study limb dose** will also be produced separately for subjects who received injections in study limb only and subjects who received injections in study limb plus any other limb (non-study upper limb and/or lower limb(s)):

- Overall summary table of all TEAEs
- TEAEs with the number and percentage of subjects and the number of occurrences presented by primary SOC and PT
- TEAEs by causality combined with intensity with the number and percentage of subjects and the number of occurrences by primary SOC and PT
- SAEs with the number and percentage of subjects with SAEs and the number of occurrences by primary SOC and PT
- TEAEWDs with the number and percentage of subjects with TEAEWDs and the number of occurrences by primary SOC and PT

Additionally, TEAEs by **study limb dose** across all Treatment Cycles 1, 2, 3, and 4 will be summarized by class of time elapsed from the last Dysport Dose injected to the event onset:

- 1-28 days (first 4 weeks)
- 29-56 days (from >4 to  $\leq$ 8 weeks)
- 57-84 days (from >8 to  $\leq 12$  weeks)

- $85-112 \text{ days (from >12 to <math>\leq 16 \text{ weeks)}$
- 113-140 days (from >16 to  $\leq 20$  weeks)
- >140 days (>20 weeks).

Futhermore, the following TEAE tables for each Treatment Cycle will be produced by **total body dose** administered in the specified Treatment Cycle using the dose groups specified in Section 3.2.1.2.:

- Overall summary table of all AEs
- TEAEs with the number and percentage of subjects and the number of occurrences presented by primary SOC and PT
- TEAEs by intensity with the number and percentage of subjects and the number of occurrences by primary SOC and PT
- TEAEs by causality with the number and percentage of subjects and the number of occurrences by primary SOC and PT
- TEAEs by causality combined with intensity with the number and percentage of subjects and the number of occurrences by primary SOC and PT
- SAEs with the number and percentage of subjects with SAEs and the number of occurrences by primary SOC and PT
- TEAEWDs with the number and percentage of subjects with TEAEWDs and the number of occurrences by primary SOC and PT
- TEAEs by treatment group, with the number and percentage of subjects with TEAEs and the number of occurrences presented by primary SOC and PT, for all TEAEs occurring for  $\geq 3\%$  of subjects and more than 1 subject in at least one treatment group at the PT level.

For Treatment Cycles 2, 3, and 4 the following tables by **total body dose** will also be produced for subjects who received injections in study limb plus any other limb (non-study upper limb and/or lower limb(s)):

- Overall summary table of all TEAEs

- TEAEs with the number and percentage of subjects and the number of occurrences presented by primary SOC and PT
- TEAEs by intensity with the number and percentage of subjects and the number of occurrences by primary SOC and PT.

## AESIs for Repeat Treatment

In addition to the summary tables by study limb dose across all Treatment Cycles 1, 2, 3, and 4 the following AESI tables for each Treatment Cycle will be produced by **total body dose** administered in the specified Treatment Cycle using the dose groups specified in Section 3.2.1.2:

- Overall summary table of all AESIs, including also an overall summary of all AEs for all treatment cycles combined
- AESIs with the number and percentage of subjects and the number of occurrences presented by primary SOC and PT
- AESIs by causality combined with intensity with the number and percentage of subjects and the number of occurrences by primary SOC and PT- .

*3.2.3.2 Physical and Neurological Examinations* 

Clinically significant changes in the physical examination findings (abnormalities) will be recorded as AEs. Details of each neurological examination will be listed, by subject ID.

## 3.2.3.3 Laboratory Data

For clinical laboratory safety tests (clinical chemistry including serum alkaline phosphatase total and bone isoenzyme, and HbA1c), all data will be listed, in standard international (SI) units, by subject ID and assessment visit, and all abnormal values will be flagged (High [H], Low [L], or clinically significant [C]).

A listing will be presented of all values for a subject with at least a clinically significant abnormal value.

A separate listing of normal ranges for SI units will be provided by gender and age where relevant.

Baseline will be defined as the last measurement collected prior to receiving the initial study treatment, Treatment Cycle 1 on Day 1. For the fixed dose Treatment Cycle 1 Baseline and Week 16 will be presented by Study Limb Dose. For Repeat Treatment Baseline and EOS/EW will be presented by Total Body Dose and subjects will be assigned to the treatment group according to the last study treatment received.

Summary statistics for all laboratory parameters by treatment group will be presented at each scheduled assessment (Baseline, Treatment Cycle 1 Week 16, and EOS/EW) for actual values and changes from baseline. The number and percentage of subjects with low, normal or high values will also be presented, for each treatment group, at each scheduled assessment. In addition, shift from Baseline tables of the number and percentage of subjects with low, normal or high values will or high values will be presented for each treatment group, at each scheduled assessment, and an overall summary of shift from baseline throughout the study will also be provided.

Results from urine and serum pregnancy tests will be listed by subject ID and assessment visit.

3.2.3.4 Vital Signs

Vital signs data (systolic and diastolic BP and HR) will be presented in a listing which will be sorted by subject ID and assessment visit. All abnormal values will be flagged (High (H) or Low (L)).

Baseline values for each treatment group will be defined as the last vital signs measurement collected prior to receiving the initial study treatment on Day 1 of Treatment Cycle 1. For the fixed dose Treatment Cycle 1 the summary table will be presented by Study Limb Dose. The tables for Repeat Treatment will be presented by Total Body Dose and subjects will be assigned to the treatment group in the designated Treatment Cycle according to the study treatment received in that cycle.

For each treatment group, summary statistics will be presented for each scheduled assessment visit, for both actual values and changes from baseline. The number and percentage of subjects with low, normal or high values will also be presented, for each treatment group, at each scheduled assessment. In addition, shift from baseline to tables of the number and percentage of subjects with low, normal or high values will be presented for each treatment group, at each scheduled assessment.

The criteria thresholds for abnormal values are presented in section 8.1.

In addition, body mass index (BMI) will be calculated using age in months at the time of the height and weight assessments. This will be included in the listing, and a shift from baseline table will present the number and percentage of subjects in Less than the 5th percentile, 5th Percentile to less than the 95th percentile, and Equal to or greater than the 95th percentile categories for each treatment group, at each scheduled assessment. The criteria for BMI normal ranges are presented in section 8.2.

### 3.2.3.5 Electrocardiogram

All available ECG data and clinical interpretations will be listed by subject ID, treatment group, and assessment visit.

Subjects will have a set of three ECG recordings taken at Screening, Week 6 of Treatment Cycle 1 and EOS/EW. For each quantitative parameter (QTcB, QTcF, QT, PR, HR, RR, and QRS) the average of these recordings will be calculated. The average measurements will be used in all summary tables. In case of missing data for one or two ECG recordings of the three expected, the average will be performed on the values available.

In the listings the individual results (raw data) and the associated calculated average will be presented.

Baseline will be defined as the average of the ECG recordings collected at the last ECG assessment prior to receiving the initial study treatment, on Day 1 of Treatment Cycle 1. For fixed dose Treatment Cycle 1 the summary table will be presented by Study Limb Dose. For Repeat Treatment Baseline and EOS/EW will be presented by Total Body Dose and subjects will be assigned to the treatment group based on the dose received in the last Treatment Cycle.

Summary statistics of all ECG parameters (except QRS axis) will be presented by treatment group for each scheduled assessment visit, for both actual values and changes from baseline.

For interpretation of clinical significance (within normal limits; abnormal, not clinically significant; abnormal, clinically significant; not evaluable), a frequency table will be presented, by treatment group, at each scheduled assessment visit. A shift table from baseline to the Treatment Cycle 1 Week 6 and to the EOS/EW visit will also be presented.

Additionally, a frequency table will be presented for the worst value of all post-dose assessments (abnormal, clinically significant > abnormal, not clinically significant > not evaluable > within normal limits). The number and percentage of subjects with duration of QT/QTc interval within the following three ranges of interest will also be presented, for both Fridericia's and Bazett's methods, by treatment group, for each scheduled assessment visit and an overall summary for any post-baseline visit:

- ≤450 msec
- >450 to 480 msec
- >480 to 500 msec
- >500 msec.

The number and percentage of subjects with an increase from baseline in the QT/QTc interval of >30-60 msec and >60 msec will also be presented, for both Fridericia's and Bazett's methods, by treatment group, for each scheduled postbaseline assessment visit and an overall summary for any post-baseline visit.

An additional listing will display any QT/QTc intervals that fall within any of the ranges of interest for either absolute value or increase from baseline as described above.

The number and percentage of subjects with any of the following ECG abnormalities will be provided by treatment group for each scheduled assessment visit:

- New morphologies
- Arrhythmias
- Second and third degree heart block
- ST segment abnormalities
- T-wave abnormalities
- U-wave abnormalities
- Myocardial infarction
- Right bundle branch block
- Left bundle branch block
- Other conduction abnormalities
- Others (except abnormalities described above).

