8.2.4 Electrocardiogram Analysis

An ECG analysis will be included as a safety evaluation/endpoint in this study.

Subjects will have a set of three 12-lead ECG recordings taken at the screening visit (considered as baseline assessment), then subsequently one 12-lead ECG at Treatment 1, Week 6 and at the end of study visit or early withdrawal. The 12-lead ECG recordings will be performed at a paper speed of 25 mm/sec, recorded with the subject supine. Analysis of the ECG results will be performed in a central laboratory.

All ECGs that are performed post-treatment will be compared to baseline. Any clinically significant difference in the ECG parameters or morphology will be noted.

If at any time point the QTc exceeds 500 msec or the change from Baseline exceeds 60 msec, the ECG will be repeated until the parameters fall below these limits or the Investigator is satisfied that the subject is not at any significant risk.

Analysis of the duration of the QT/QTc interval, the HR and the presence of any of the following ECG abnormalities: new morphologies, arrhythmias, second degree AV block, third degree AV block, ST segment abnormalities, T-wave abnormalities, U-wave abnormalities, myocardial infarction, right bundle branch block, left bundle branch block, will be performed. These and any other clinically relevant abnormality will also be reported by the central provider to the Investigator and recorded as an AE.

The QT interval is defined as the time (in msec) from the beginning of the QRS complex to the end of the T-wave on the ECG. The QTc is defined as the corrected QT interval using the Fridericia and the Bazett formula. The duration of the QT/QTc interval in the ECGs taken for each subject and at each time point will be used for the analysis.

In summary, the ECG safety endpoints will include:

- Duration of the QT/QTc interval (in msec) at each ECG time point.
- Mean change from Baseline in the duration of the QT/QTc interval at each ECG time point.
- Proportion of subjects at each ECG time point with a duration of QT/QTc interval of: >450 to 480 msec, >480 to 500 msec and >500 msec.
- Proportion of subjects at each ECG time point with an increase from baseline in the QT/QTc interval of >30 msec and >60 msec.

- Proportion of subjects with any of the above listed ECG abnormalities at each ECG time point.

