The GAS for each goal will be evaluated post-baseline at Week 6 and Week 16 of each Treatment Cycle, and also at the EOS/EW, and the total GAS score will be calculated using the formula in Section 3.2.13.20. A total GAS score of 50 means all individual goals have been achieved as expected.

Paediatric Quality of Life (PEDsQL) Inventory: Parents/guardians will be asked to complete questionnaires on their child's QoL [15] at each post-treatment visit to the study centre except Week 6. The PedsQL parent inventory measures healthcare concepts for children/adolescents of ages 2 to 18 years of age [16]. The Generic Core Scales cover four multidimensional scales including physical, emotional, social and school aspects with three

summary scales of total scale score, physical health summary score and psychosocial health summary score.

Parents/guardians will also complete the Condition-specific Module in CP (in countries where translation is available) [16], which is a complement to the Generic Core Scale of the PedsQL. It is designed to provide greater measurement sensitivity for circumscribed populations. The answers to the questionnaire will be obtained at baseline, at Week 16 of Treatment Cycle 1, and at the EOS/EW.

- For each defined scale a score is calculated using the transformations in Section 3.2.13.21.
- 1.3.2.2 Safety Assessments
  - Adverse Events (AEs): Collected from the signing of informed consent up until the EOS.
  - Physical examination: A physical examination will be carried out by a physician or by another qualified staff member designated by the Investigator at the screening visit and at the EOS/EW. If in the opinion of the Investigator there are any clinically significant changes in the physical examination findings (abnormalities) they will be recorded as AEs.
  - Vital signs: Systolic and diastolic blood pressure (BP), and heart rate (HR) will be measured at each visit to the study centre. Blood pressure will be measured with the subject in a sitting position.
  - Electrocardiogram (ECG): Subjects will have a set of three 12-lead ECG recordings taken at the screening visit (considered as baseline assessment), then subsequently one 12-lead ECG at Treatment Cycle 1, Week 6 and at the EOS/EW. The 12-lead ECG recordings will be performed at a paper speed of 25 mm/sec, recorded with the subject supine. Analysis of the ECG results will be performed in a central laboratory.

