#### **Safety**

If a value required a retest (for laboratory values, vital signs and ECG) the closest non-missing reliable value to the scheduled visit will be used in the summary tables. An assessment will be considered reliable if it is performed without any technical problem and if the result is within the range of plausible values.

For adverse events with missing information for the intensity and causality the value will not be replaced and will be summarised as a separate category.

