## 3.2.13.22 Electrocardiogram Average Result

For each quantitative ECG parameter the average result at each visit will be calculated as follows:

Average ECG result = sum of non-missing results at that visit / number of non-missing results at that visit.

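### SAP 3.2.3.5 assumes three ECGs at every visit against a scheduled one after dosing, and neither of its two unranked rules for repeats reliably keeps a triggering QTc reading in the >500 or >60 msec tables.

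*SAP*

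**What the plan says.** Protocol 8.2.4 takes three 12-lead ECGs at screening as baseline, "then subsequently one 12-lead ECG at Treatment 1, Week 6 and at the end of study visit or early withdrawal". SAP 1.3.2.2, summarising the protocol, agrees: "then subsequently one 12-lead ECG at Treatment Cycle 1, Week 6 and at the EOS/EW".

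SAP 3.2.3.5 differs: "Subjects will have a set of three ECG recordings taken at Screening, Week 6 of Treatment Cycle 1 and EOS/EW". It treats one or two recordings out of three as missing data, averages what is available, and states: "The average measurements will be used in all summary tables". SAP 3.2.13.22 defines that average as "sum of non-missing results at that visit / number of non-missing results at that visit", with no cap at three and no exclusion of repeats. SAP section 5 (Changes from Protocol) does not mention a change in the number of ECGs.

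Under protocol 8.2.4, if QTc exceeds 500 msec or rises more than 60 msec from baseline, "the ECG will be repeated until the parameters fall below these limits", or until the investigator is satisfied that the child is not at significant risk. The protocol describes no other reason to repeat an ECG.

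SAP 3.2.4.1 (Safety) has its own rule for retests and names ECGs among them: "the closest non-missing reliable value to the scheduled visit will be used in the summary tables". SAP 3.2.14 applies similar closest-value logic where several records fall in an interval that expects one.

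**The concern.** The proportions of children above 500 msec and with a rise above 60 msec are stated ECG safety endpoints in protocol 8.2.4, by time point. The repeats available to the analysis exist because the first reading crossed one of those limits, and they tend to end on a lower value. A rule that averages them with the trigger, or lets a later reading replace it, works against the count that the table is meant to give.

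The count of three also affects which rule applies. SAP 3.2.14 operates only where one assessment is expected. With one ECG expected at Week 6, a repeat in the window engages it. With three expected, a second recording looks like part of the set and is averaged. Two programmers could therefore produce different outlier tables from the same data, both following the SAP.

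**Working it through.** The plan states no figure for QTc outliers, so there is nothing to reproduce first.

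**1. ECGs per visit**

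| Source | Screening | Week 6 | End of study / early withdrawal |
|---|---|---|---|
| Protocol 8.2.4 | 3 | 1 | 1 |
| SAP 1.3.2.2 | 3 | 1 | 1 |
| SAP 3.2.3.5 | 3 | 3 | 3 |

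**2. Averaging rule (SAP 3.2.13.22), repeat filed under the same visit.** Value used = sum / number. The readings are illustrative.

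- 515 and 475: 990 / 2 = 495, tabulated in >480 to 500. Lost from >500.
- 510 and 485: 995 / 2 = 497.5. Lost.
- 530 and 475: 1005 / 2 = 502.5. Kept.
- Changes of +65 and +40: 105 / 2 = +52.5, tabulated in >30 to 60. Lost from >60.
- Changes of +65 and +58: 123 / 2 = +61.5. Kept.

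With one repeat, a reading above 500 is lost exactly when the two values sum to 1000 or less.

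**3. Closest-value rule (SAP 3.2.4.1) at Week 6.** SAP Table 10 gives Days 39 to 47, centre Day 43. If the first ECG is on day d and the repeat L days later, the repeat replaces it when |d + L − 43| < |d − 43|.

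- L = 1: replaced for d = 39 to 42 (4 of 9 days), kept for d = 43 to 47 (5 of 9).
- L = 2: replaced for d = 39 to 41 (3 of 9), tie at d = 42.
- L = 0: a tie on every day, and the SAP gives no tie-break.

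**4. Size under averaging.** The documents give no QTc mean or SD, so these inputs are assumptions. Readings are normal around a fixed true visit QTc. Among first readings above 500, the ECG is repeated until one reading is 500 or less, and all are averaged. Share whose average stays above 500, at reading SD 12 msec:

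| True QTc (msec) | Share kept |
|---|---|
| 480 | 8% |
| 490 | 30% |
| 500 | 68% |
| 505 | 85% |
| 510 | 94% |
| 520 | 99.6% |

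At SD 8 and 20 the shares are 17% and 44% for a true QTc of 490, 90% and 79% for 505, and 98% and 87% for 510.

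A second simulation assumed a population mean of 415, between-subject SD 20, within-visit SD 8 to 16, true-shift SD 10 to 20 msec and up to ten repeats. About 36 to 81% of initial values above 500, and 47 to 95% of initial changes above 60, averaged to or below the limit. The second range omits one setting with only 10 events. The width of both ranges shows how far the result depends on the inputs. They are not estimates for this trial.

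**The case against.** The strongest reply is that a triggered repeat is a retest, that SAP 3.2.4.1 names ECG retests, and that a specific rule overrides a general formula. On that reading SAP 3.2.3.5 averages only its expected set, and a lone post-dose ECG is simply its own average. This is a reasonable reading, but the SAP does not state it, and step 3 shows that the closest-value rule can still lose the trigger, by substitution.

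The documents also do not say whether repeats are filed under the scheduled visit. If they are recorded as unscheduled, they may enter neither rule. The point depends on that convention, which should be written down.

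Mitigations exist. SAP 3.2.3.5 lists individual results beside the average, adds a listing of QT/QTc intervals in the ranges of interest, and tabulates the worst post-dose clinical interpretation. Clinically significant ECG findings can also be recorded as adverse events. However, the text does not say whether the range listing works from individual or averaged values, and listings do not give proportions by dose group.

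A reader might infer that the SAP systematically removes genuine exceedances. The documents do not support that. Averaging is not the only rule, repeating may stop because the investigator is satisfied rather than because a value is low, and step 4 shows heavy loss only where the true QTc is below 500 and the first reading was high by noise. A reader might also infer that three baseline recordings against one post-dose recording makes change from baseline noisier than the SAP assumes. The SAP states no such variance, and the asymmetry is the protocol's own design, which the fix leaves in place.

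**Conclusion.** The ECG count in SAP 3.2.3.5 is wrong against protocol 8.2.4 and against SAP 1.3.2.2, and the difference is not declared in section 5. The SAP has two rules for repeated ECGs without precedence, and neither reliably keeps a triggering reading in its category. This rests on repeats being filed under the scheduled visit, which the documents neither state nor exclude.

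The number of children affected cannot be derived from the documents. Under the assumptions in step 4, most noise-driven readings just over 500 would leave the >500 category under averaging, and most readings from children whose true QTc exceeds 500 would stay. The loss is confined to the summary tables. It is still worth correcting, because these tables report a pre-specified paediatric safety endpoint and the averaging rule tends to under-count.

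**What to change.** - Correct SAP 3.2.3.5 to three recordings at screening and one at Week 6 and at end of study or early withdrawal. Average only the screening set, for baseline.
- In the QT/QTc category tables, classify the scheduled recording at each visit.
- State that threshold-triggered repeats do not enter an average (3.2.13.22) and do not replace the triggering value under 3.2.4.1 or 3.2.14. State how repeats are assigned to visits.
- Base the any-post-baseline row on the worst recorded value. The protocol does not prescribe this, but it matches the worst-value table that SAP 3.2.3.5 already plans for clinical interpretation.

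The cost is SAP wording and programming, with no new ECGs. Outlier counts may look slightly less favourable and will include some readings that were high by noise. The listing of individual results lets a reader see which exceedances were not confirmed on repeat.
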